7.8 UNSCHEDULED FOLLOW-UP

Any unscheduled return visits to the study center/Principal Investigator for non-standard of care evaluation for ongoing Achilles-related issues will be documented. Visits required by the protocol or visits for routine post-operative follow-up are not considered unscheduled and do not need to be reported as an unscheduled visit.

7.9 REVISION/ADDITIONAL ACHILLES SURGERY

If the subject has additional or revision Achilles surgery on the index Achilles at any time during the follow-up period, the clinical site should make every effort to collect the procedure/operative notes for the procedure and complete the Revision/Additional Achilles Surgery.

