4.1 SAMPLE SIZE

Up to 10 subjects will be enrolled and treated with the Rotation Medical Bioinductive Impant at Union Memorial hospital and the associated Surgery Center.

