4.3 PRIMARY OUTCOME MEASURES

4.3.1 Increase in Tendon Thickness

Achilles tendon thickness will be measured pre-operatively (baseline) and the total thickness of the tendon and any newly induced tissue at the implant site will be measured at each follow-up visit using magnetic resonance imaging (MRI). The mean (\pm SD) change in post-operative Achilles tendon thickness will be calculated at each follow-up interval.

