5 STATISTICAL ANALYSIS PLAN

This is an initial feasibility study and not powered to address the hypotheses. Changes in tendon thickness over the time of the follow up visits will be assessed by a Repeated Measures ONEWAY ANOVA with a post hoc Scheffe. Indices of new tissue integration and maturation at each follow up visit will be assessed by Chi Square analyses.

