6 ELIGIBILITY CRITERIA

Subjects who meet all inclusion criteria (Section 6.1) and none of the exclusion criteria (Section 6.2) will be eligible to participate in the study.

Enrollment in the study occurs upon intra-operative confirmation that the subject meets all of the inclusion criteria and none of the exclusion criteria. Subjects who meet eligibility criteria and are enrolled will be followed per protocol through the end of the study (i.e., intent-to-treat). Subjects who do not meet the study eligibility criteria at the time of surgery will not be enrolled.

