12 RISKS AND BENEFITS

12.1 RISKS AND RISK MITIGATION

Study patients will be informed of all known potential side effects and complications associated with the study assessments and study procedure prior to enrollment in the study.

There are no known incremental risks to the subject for participating in the study. The risks associated with participating in this study are the same as if the patient is treated outside of the study using the same commercially-available device and include the following potential risks of Achilles Tendinopathy surgery performed under general or regional anesthesia:

- Tissue inflammation
- The need for repeated surgery because tendons do not heal properly or tears
- Pain or stiffness that won't go away
- Fever and/or infection
- Complication from anesthesia
- Nerve or blood vessel damage
- Adverse reaction to device

In addition, subjects will be required to undergo MR imaging. MRI is generally a well-tolerated procedure and there is no ionizing radiation involved with MR imaging. The potential risks are minimal and include claustrophobia, coil element heating and peripheral nerve stimulation, although the latter two are considered highly unlikely, given that the subjects will be imaged within preset safety guidelines to eliminate peripheral nerve stimulation. Coil element heating ranges from a mild sensation of heat to a potential burn. This is considered highly unlikely, as the coils have all undergone extensive testing and clinical use, and special pads are placed surrounding all contact points.

All Investigators will undergo training and subjects will be screened and evaluated for medical histories/conditions that may compromise safe, successful completion of any of the study assessments or performance of the device. Subjects with a known hypersensitivity to bovine-derived materials will not be enrolled in the study.

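### The plan does not separate MRI taken after revision or additional Achilles surgery, so the thickness and integration outcomes can mix effects of a second operation with effects of the implant

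*Combined protocol and SAP*

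**What the plan says.** Section 7.9 is the only section devoted to further surgery. For the case "If the subject has additional or revision Achilles surgery on the index Achilles at any time during the follow-up period" it asks the site to try to obtain the operative notes and to complete the revision record. Table 7-1 and Section 7.7 require such surgery to be reported at each follow-up visit. None of these places mentions the MRI scans that follow it.

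The follow-up rules keep the subject in the study. Section 6 states: "Subjects who meet eligibility criteria and are enrolled will be followed per protocol through the end of the study (i.e., intent-to-treat". Section 7.2 makes withdrawal of consent the only exception. Section 7.7 schedules an MRI for all subjects at 3 months, 1 year and 2 years.

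The imaging outcomes use every visit. Under Section 4.3.1, "the total thickness of the tendon and any newly induced tissue at the implant site will be measured at each follow-up visit", and the mean "change in post-operative Achilles tendon thickness will be calculated at each follow-up interval". Section 4.3.2 assesses integration and maturation of the new tissue at each post-operative MRI. Section 5 names a repeated measures ANOVA for thickness and chi-square analyses for integration and maturation. It gives no rule for scans after a second operation: no exclusion, no failure assignment and no sensitivity analysis.

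**The concern.** The objective in Section 3 is to evaluate bioinduction of new tissue and tendon healing after implantation. Thickness and integration are the primary measures that carry this. Thickness is the total at the implant site, so it cannot distinguish tissue induced by the implant from tissue added or removed at a second operation. The integration score is likewise read on a site that may have been operated on again.

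The case is foreseeable. Section 12.1 lists among the risks: "The need for repeated surgery because tendons do not heal properly or tears". The study has one arm and is small ("Up to 10 subjects will be enrolled and treated"), so there is no control group in which the same effect could be seen, and one subject carries visible weight. If the rule is chosen only after the scans have been read, the choice itself can move a primary result.

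**Working it through.** The plan states no figure to reproduce. Section 5 says: "This is an initial feasibility study and not powered to address the hypotheses". The figures below are illustrations.

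**Inputs**
- n = up to 10 subjects (Section 4.1).
- Scale for thickness: a gain of about 2.5 mm in sheep (Section 1), the only thickness gain in the documents.
- d = thickness difference (mm) that the second operation causes in that subject's scan. The documents give no value. Assumed range: -2.5 to +5 mm.
- Rate of further Achilles surgery: not given. Assumed range: 2% to 20%.

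**Step 1: do the scans enter the summaries?** Sections 6, 7.2 and 7.7 mean that the scans are made. Sections 4.3.1 and 4.3.2 summarise each visit. Sections 5 and 7.9 remove nothing. Inclusion is therefore the default, by silence and not by a stated rule.

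**Step 2: shift in a visit mean.** Let m be the mean change of the other 9 subjects and c the change the affected subject would have shown without the second operation.
- Mean with the scan: (9m + c + d)/10.
- Mean without the effect of the second operation: (9m + c)/10.
- Shift: d/10.

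| Analysed subjects | d = -2.5 mm | d = +2.5 mm | d = +5 mm |
|---|---|---|---|
| 10 | -0.25 | +0.25 | +0.50 |
| 8 | -0.31 | +0.31 | +0.63 |
| 6 | -0.42 | +0.42 | +0.83 |

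At n = 10 the range runs from -0.25/2.5 = -10% to +0.50/2.5 = +20% of the sheep gain.

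**Step 3: what setting the scan aside does.** The mean becomes m, so the two summaries differ by (c + d - m)/10. This equals d/10 only if c = m. For example, take m = 2.5, c = 0 and d = +2.5 mm, all assumed. The mean with the scan is (22.5 + 2.5)/10 = 2.5 mm and the mean without it is also 2.5 mm. The mean without the surgery effect would have been 22.5/10 = 2.25 mm. Dropping the scan alone is therefore not a cure, because it can favour the subjects who did well.

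**Step 4: integration and maturation.** On a yes/no item one subject is 1/10 = 10 percentage points, or 1/8 = 12.5 with 8 readable scans.

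**Step 5: how likely is at least one case?** The formula is 1 - (1 - p)^10. For p = 2%, 5%, 10% and 20% it gives 18%, 40%, 65% and 89%. The earlier clinical study in Section 1 reports one further operation among 24 subjects. That rate gives 1 - (23/24)^10 = 35%, but the study was in the shoulder and is only a rough guide.

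**The case against.** A reader might infer that tissue from a failed case is counted as implant-induced gain, so that the bias favours the device. The documents do not support that:

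- No section says that revised subjects stay in the analysis or that repair tissue is to be scored as induced tissue. Section 7.10 lets the investigator withdraw a subject. However, this applies only in the subject's interest, and the same section asks for efforts to retain subjects, so it does not close the gap.
- The sign is open. Section 7.5 shows that surgery can add tissue, by weaving a second tendon into the Achilles. Section 1 says debridement can leave the tendon compromised.
- Nothing says a second operation removes the boundary scored under Section 4.3.2. A site operated on again could score worse.

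A failed case is also not hidden. Further surgery is reported at each visit, invasive surgery to fix a problem meets the serious adverse event definition in Section 8.2, and tear rate is a separate primary measure. This stands as far as safety goes. It does not correct the thickness mean or the integration score.

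Two objections bear on the remedy, and both stand. Calling every additional operation an integration failure would be too broad: in the earlier study in Section 1, a bursal clean-up was followed by healing and tissue induction described as unaffected. And a thickness summary that only drops failed cases selects for successes and fits poorly with the intent-to-treat wording in Section 6.

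Finally, total thickness is non-specific even without a second operation, because the index procedure itself includes debridement and possibly a tendon transfer. That is a separate limitation and no reason to leave this one open.

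**Conclusion.** The concern holds as a gap with an unknown direction of bias. Followed as written, the plan lets scans taken after a second operation on the tendon or implant site enter the visit-level thickness and integration results with nothing to mark them. For one affected subject among 10, the shift in mean thickness change is -0.25 to +0.50 mm for an assumed d of -2.5 to +5 mm, and a yes/no integration item can move by 10 percentage points. These sizes depend on a second operation occurring, for which no Achilles rate is given, and on d, for which the documents give no value. The stronger inference, that the plan systematically credits repair tissue to the implant, is not supported. The study is unpowered, so no sample-size or power figure changes. What changes is what the primary imaging results can be said to show.

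**What to change.** Amend Sections 4.3.1, 4.3.2 and 5, before results are seen, to state that:

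1. Subjects with revision or additional surgery on the index Achilles remain in follow-up, with scheduled MRI.
2. Every MRI taken after such surgery is flagged, and the number of revised subjects is reported beside each primary result.
3. Visit-level thickness change and integration/maturation are each presented with and without the flagged scans. Flagged scans are not cited as evidence of implant-induced tissue.
4. For integration/maturation, the subject counts as not achieved at later visits only when the surgery involved the tendon or implant site. Other additional surgery, such as a bursal debridement, is listed separately.
5. Thickness is analysed with a mixed model for repeated measures. Classical repeated measures ANOVA uses complete cases, so setting aside one scan would drop the whole subject, 1 of 10.

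The cost is protocol and SAP wording and a second version of each summary. The reports and operative notes needed for the flag are already collected, and clinical management does not change. The downside is slightly fewer late scans in one of the two thickness summaries, and possible selection there towards subjects who did not fail. Both summaries are shown for that reason. As Step 3 of the working shows, their agreement would not by itself prove the absence of bias.

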7.10 EARLY WITHDRAWAL OR LOST TO FOLLOW-UP

If a subject wishes to withdraw from the study at any time, (s)he is able to do so voluntarily without having to justify it and without affecting her/his relationship with the Investigator.

Also, an Investigator may withdraw a subject from the study at any time if (s)he thinks it is in the subject's best interest.

The subject's future management will not be changed by a decision, voluntary or otherwise, to withdraw from the study.

All reasonable efforts should be made to retain the subject in this clinical study until completion of the clinical assessments at each follow-up visit. A subject will be considered "lost to follow-up" after a minimum of 2 documented phone calls to the subject were completed by a member of the study staff and a certified letter was sent to the last known address by a traceable method (e.g., certified mail; courier; commercial shipping/transport company).

7.11 END OF STUDY

Subjects will be exited upon successful completion of follow-up assessments or at the time of withdrawal or lost-to-follow-up.

8 ADVERSE EVENT DEFINITIONS AND REPORTING

Adverse events are to be reported from the time of enrollment through the last study follow-up visit.

8.1 DEFINITION OF ADVERSE EVENT (AE)

An Adverse Event (AE) is any undesirable clinical occurrence experienced by the subject. Any underlying disease that was present at the time of enrollment and prior to surgery that persists after surgery is not considered an AE.

8.2 SERIOUS ADVERSE EVENT (SAE)

A Serious Adverse Event (SAE) includes any of the following events:

- Results in death
- Is life threatening
- Requires subject hospitalization or prolongation of existing hospitalization
- Requires invasive surgical intervention to fix the problem
- Results in persistent or significant disability/incapacity
- Is considered an important medical event

An important medical event that may not meet one of the above definitions might be considered as an SAE if it jeopardizes the health of the subject or requires surgical intervention to prevent one of the outcomes listed in the above definition. Elective hospitalization after the procedure that was planned prior to subject enrollment is not to be considered as an SAE.

8.3 UNANTICIPATED ADVERSE DEVICE EFFECT (UADE)

An Unanticipated Adverse Device Effects (UADE) is any serious adverse effect on health or safety, or any life-threatening problem or death caused by, or associated with, a device, if that effect was not previously identified in nature, severity, or degree of incidence in protocol, subject informed consent form, or application, or any other unanticipated serious problem associated with a device that relates to the rights, safety, or welfare of subjects. Anticipated adverse events are listed as known risks in **Section 12.1**.

8.4 ASSESSING, RECORDING AND REPORTING AES, SAES, AND UADES

Only non-serious AEs that are classified by the Investigator as either device-related or procedure-related will be reported. All SAEs, regardless of relationship to the Rotation Medical Bioinductive Implant, and all UADEs will be reported.

An AE may be volunteered spontaneously by the subject or discovered as a result of questioning or physical examination by the Investigator or study staff. The following information should be reported on the Adverse Event CRF as soon as the Investigator becomes aware of the event and updated as needed until event resolves:

- Date of AE onset
- Date the Investigator became aware of the AE
- Main complaints/symptoms of the AE
- Relationship to the study device
- Relationship to the study procedure
- Status of the adverse event

Source documents (e.g., procedural notes, treatment notes, or a signed clinical summary) may be required as supporting documentation for the reported AE.

9 MALFUNCTIONS

Failure of the Rotation Medical Bioinductive Implant to meet its performance specifications or to perform as intended will be documented on the Malfunction CRF. In the event of a malfunction, every effort must be made to return the suspected Rotation Medical device or instrument to the Sponsor for analysis. Malfunctions will be evaluated for reportable requirements through the FDA medical device reporting (MDR) system.

10 PROTOCOL DEVIATIONS

Investigators are required to adhere to the study protocol, signed Clinical Trial Agreement (CTA), applicable national or local laws and regulations, and any conditions required by the appropriate IRB/EC or applicable regulatory authorities.

A protocol deviation is used to describe situations in which the protocol was not followed (this includes all activities at each scheduled visit or activities occurring outside of the study windows). All attempts should be made to obtain Sponsor approval of the deviation prior to their occurrence.

An Investigator must notify the Sponsor and the reviewing IRB/EC of any deviation from the Study Protocol that was done to protect the life or physical well-being of a subject (medical emergencies). Such notice should be given within 5 days of the occurrence. The Sponsor will determine if the subject affected is to continue in the study.

Documentation of deviations identified by the investigational center, the monitor, or other Sponsor representative(s) will be entered into the Protocol Deviation CRF for the purpose of tracking Investigator compliance with the protocol. The investigational center will be required to document actions taken to prevent recurrence of deviations. The Sponsor representative will initiate corrective actions based on individual deviations or trending reports as appropriate.

11 REPORTING REQUIREMENTS

Table 11-1 shows a summary of all reporting requirements. In addition to this list, individual IRBs may add additional reporting requirements and/or require a different notification time frame.

Table 11-1: Summary of Reporting Requirements

Type of Report	Prepared by Investigator FOR	Notification Time Frame
Death ¹	Sponsor & IRB	Within 24 hours of knowledge
Withdrawal of IRB approval	Sponsor	Within 5 working days of knowledge
Protocol Deviation to Protect Subject Life or Physical Well-Being	Sponsor & IRB	Within 5 working days of knowledge
Unanticipated Adverse Device Effect (UADE)	Sponsor & IRB	Within 10 working days of knowledge

¹Copies of death records, medical records for the events that led to the subject's death, a death certificate (if available), and an autopsy report (if performed) should be requested.

12 RISKS AND BENEFITS

12.1 RISKS AND RISK MITIGATION

Study patients will be informed of all known potential side effects and complications associated with the study assessments and study procedure prior to enrollment in the study.

There are no known incremental risks to the subject for participating in the study. The risks associated with participating in this study are the same as if the patient is treated outside of the study using the same commercially-available device and include the following potential risks of Achilles Tendinopathy surgery performed under general or regional anesthesia:

- Tissue inflammation
- The need for repeated surgery because tendons do not heal properly or tears
- Pain or stiffness that won't go away
- Fever and/or infection
- Complication from anesthesia
- Nerve or blood vessel damage
- Adverse reaction to device

In addition, subjects will be required to undergo MR imaging. MRI is generally a well-tolerated procedure and there is no ionizing radiation involved with MR imaging. The potential risks are minimal and include claustrophobia, coil element heating and peripheral nerve stimulation, although the latter two are considered highly unlikely, given that the subjects will be imaged within preset safety guidelines to eliminate peripheral nerve stimulation. Coil element heating ranges from a mild sensation of heat to a potential burn. This is considered highly unlikely, as the coils have all undergone extensive testing and clinical use, and special pads are placed surrounding all contact points.

All Investigators will undergo training and subjects will be screened and evaluated for medical histories/conditions that may compromise safe, successful completion of any of the study assessments or performance of the device. Subjects with a known hypersensitivity to bovine-derived materials will not be enrolled in the study.

12.2 BENEFITS

Participation in this study is voluntary. Subjects can obtain the same treatment without participating in this study. However, information gathered from this study will help the Sponsor to continue to evaluate long-term performance of the device.

13 DATA MANAGEMENT

13.1 DATA COLLECTION

Report forms will be completed by the Investigator (or authorized study personnel) for each subject enrolled in the study. Data queries and edit checks will be used to reconcile discrepancies between data on the source documents and data entered on the CRFs. The Investigator must assure the accuracy and completeness of the recorded data. For the purpose of this study, the ASES and Constant shoulder surveys, as well as the Recovery/Satisfaction form, may act as their own source data.

13.2 DATA PROCESSING

All study documentation will be entered and maintained in a central database by the Sponsor or Sponsor-authorized representatives. Automatic and/or manual edit checks will be issued as necessary to correct discrepant data. Appropriate quality control measures will be established to ensure accurate and complete transfer of information from the study documentation to the central database. Data files will be exported from the central database for statistical analyses.

14 ADMINISTRATIVE RESPONSIBILITIES

14.1 SITE AND INVESTIGATOR SELECTION

Each site and Investigator selected to participate will be evaluated to ensure each has the capacity, volume of surgical candidates, and capability to comply with all informed consent and protocol requirements. Each study site and Investigator are required to comply with applicable local legal and regulatory requirements and applicable U.S. federal regulations.

14.2 TRAINING

The principal investigators must be Board Certified orthopaedic surgeons with experience performing surgery for insertional Achilles tendinopathy. Prior to first enrollment, each participating surgeon will complete Sponsor-provided training on the Rotation Medical Bioinductive implant System.

The Sponsor will also be responsible for ensuring each site and Investigator are properly trained on the study protocol and applicable regulatory requirements.

To insure uniform data collection and protocol compliance, the Sponsor or Sponsorauthorized representatives will train the Study Coordinator(s) and study staff on all

components of the study including the study protocol, techniques for the identification of eligible subjects, instructions for data collection during the procedure, and schedules for follow-up.

